6.9 Adverse Event Reporting

An adverse event will be defined as follows: “Any untoward medical occurrence in a patient or clinical investigation subject administered a pharmaceutical product and which does not necessarily have a causal relationship with this treatment. An adverse event (AE) can, therefore, be any unfavorable and unintended sign, symptom, or disease temporally associated with the use of a medicinal (investigational) product, whether or not related to the medicinal (investigational) product” (ICH 1.2). As the antibacterial topical agents are given for a 7-day course, AEs will only be recorded temporarily near the time of medication administration (within 10 days of the last dose utilized). Adverse events will be identified by patient interviews during medical follow-up visits by a study investigator.

Since the study only utilizes topical antibacterial agents, abnormal laboratory values will not be recorded as AE's.

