Patients who are colonized with MRSA and who reside locally to the medical treatment facility and are able to return to the clinic will have repeat swabs (five swabs from sites listed above) every month (+/- 7 days). A month will be specifically defined as 28 days. Those who have repeat positive colonization swabs during this initial 6 month follow-up period will be observed. This data will assess the efficacy of decolonization procedures on MRSA carriage rates. Patients who are not local to the clinic will not have these repeat swabs performed, but rather will be seen at the next scheduled 6 month study visit. Adherence to the study medications will be assessed at the next scheduled study visit by a patient questionnaire (refer to case report forms). Each time a patient has a positive isolate for MRSA or MSSA, this will be frozen and saved for molecular analysis to determine the most common molecular types colonizing HIV patients and to determine if patients acquire new strains or remain colonized with the same strain over time.

All study patients (both those initially found to be colonized with MRSA and those with negative colonization swabs) will be re-evaluated in six month intervals ($+/- 2$ months) until the end of the study. Patients found to be positive at these subsequent 6 month intervals, will be randomized again, treated and followed as described above. During the last study visit (at the 2-year time period), patients will have swabs, but not undergo randomization. Hence, every 6 months, patients positive during that visit for MRSA colonization will be re-randomized in a 1:1 double-blinded fashion to mupirocin (Bactroban®) nasal ointment twice daily for seven days plus hexachlorophene (pHisoHex®) washes with showering once daily for seven days or to a placebo nasal ointment (white petroleum) and a placebo body soap with no antimicrobial activity for seven days. Repeat randomization will occur every 6 months for those carrying MRSA. For example, some patients initially randomized to receive Bactroban® and pHisoHex®, may later be randomized to the placebo arm, and vice versa.

Begin at the top of diagram again every 6 months ($+/- 2$ months). If patient is found to be positive on swabs, they are re-randomized to one of the two treatment groups for every 6-month positive swab.

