will be reported to the study lead PI using this unique identifier, together with a SAMMC-assigned identifier. These data will be utilized to characterize the MRSA isolates colonizing and infecting HIV patients, understanding the relationship between colonizing and infection-related isolates, and to determine if HIV patients acquire new strains or remain colonized with the same strain over time.

The primary endpoint of the study is the effectiveness of decolonization procedures with application hexachlorophene (pHisoHex®) soaps and nasal mupirocin (Bactroban®) compared to placebo among patients found to be colonized with MRSA in the prevention of future colonization with MRSA. As a secondary part of the study's objectives, we will also examine the effectiveness of these decolonization procedures on infections with MRSA and on soft tissue infections.

The following assessments will be performed:

a. Clinical (Visits 1, 2, 3, 4, 5, unscheduled visits)

1. Informed Consent (visit 1 only)
2. Patient Questionnaires regarding medical history, medication use, and potential risk factors for MRSA
3. Demographics (visit 1 only)
4. Review of patients medical record by study coordinators
5. Study medication dispensing (unscheduled visits for positive MRSA colonization only)
6. Adverse event review (unscheduled visits in which patient receives a study medication only)
7. Medication adherence questionnaire (visit following decolonization therapy)

b. Laboratory Values (Visits 1, 2, 3, 4, 5, unscheduled visits)

1. Swabs for MRSA colonization of the nares, throat, groin, axilla, and perirectal areas (5 swabs)
2. Pregnancy test (visit 1; visits for MRSA colonization before decolonization medications are prescribed for women of childbearing age)
3. CD4 count and HIV viral load (MRSA or soft tissue infection visit only)
4. Blood cultures (two sets) at the physician's discretion (MRSA or soft tissue infection visit only)
5. Wound culture (MRSA or soft tissue infection visit only)

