APPENDIX D: SCHEDULE OF EVENTS

Event	Visit 1	Visit 2	Visit 3	Visit 4	Visit 5	Positive MRSA Colonization visit	MRSA Colonization Follow-up visit	MRSA/Soft Tissue Infection Visit	Additional / Unscheduled Visit
Study Month (Window: months)	0	6 (±2)	12 (±2)	18 (±2)	24 (±2)				
Informed Consent	X								
Inclusion/Exclusion Criteria	X								
Urine Pregnancy Test for women of childbearing age	X					X [#]		X [#]	
Enrollment	X								
Questionnaires including Medical History, Medications and MRSA Risk Factors	X	X	X	X	X	X		X	
Demographics	X								
MRSA Swabs for Colonization	X	X	X	X	X		X	X	
Randomization*						X		***	
Dispense Drug*						X		***	
AE Review***							X		X
Drug Accountability							X		
CD4 count/HIV Viral Load**								X	
Wound Culture and possibly blood cultures****								X	
Study Completion					X				

[#]Pregnancy test will only be performed at the MRSA colonization and infection visits among women who found to be colonized with MRSA; those with a positive pregnancy test will not receive the study medications and will be terminated from the study.

*Randomization into the mupirocin (Bactroban®) and hexachlorophene (pHisoHex®) soaps or to the placebo arm will only occur if a patient has a positive colonization swab for MRSA. Patients will be randomized in a 1:1 double-blinded fashion into these groups. Patients with colonization, regardless of the group assigned, will have repeat swabs for MRSA performed monthly (+/- 7 days) for six consecutive months. For patients with repeat positive MRSA colonization swabs on the 6-month visits, will be re-randomized during each of these events.

**AE review will occur among patients given mupirocin (Bactroban®) and hexachlorophene (pHisoHex®) or the placebo ointment and soap. AE's will be assessed that are temporally associated with study medications.

***Patients who are also found to have positive colonization swabs in addition to an infection will be randomized to one of the two treatment groups if this patient was not already randomized and the same procedures for a positive colonization visit will be followed.

****Patients presenting with a soft tissue infection will have wound cultures obtained if possible. Blood cultures also may be obtained at the primary treating physician's discretion

XVIII. ATTACHMENTS

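### Sections 6.3, 6.9 and Appendix D disagree on when adverse events are reviewed, and for treated non-local patients no scheduled visit after exposure is assured to include that review

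*Combined protocol and SAP*

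**What the plan says.** Three places in the protocol set the timing of adverse-event (AE) review.

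- **Section 6.9** gives the recording window: "AEs will only be recorded temporarily near the time of medication administration (within 10 days of the last dose utilized". The next sentence gives the method: "Adverse events will be identified by patient interviews during medical follow-up visits by a study investigator". It does not say which visits these are.
- **Section 6.3, list of clinical assessments, item a.6** reads: "Adverse event review (unscheduled visits in which patient receives a study medication only".
- **Appendix D** marks AE review in two columns, the MRSA colonization follow-up visit and the additional/unscheduled visit. The row is blank for Visits 1 to 5, for the positive-colonization visit where drug is dispensed, and for the infection visit. A footnote says "AE review will occur among patients given mupirocin (Bactroban®) and hexachlorophene (pHisoHex®) or the placebo ointment and soap" and adds that "AE's will be assessed that are temporally associated with study medications".

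The monthly colonization follow-up visits are for patients who live near the facility (sections 5.1 and 6.3). Non-local patients "will not have these repeat swabs performed, but rather will be seen at the next scheduled 6 month study visit". The Appendix D footnote on monthly swabs has no such exemption; it covers colonized patients in either arm.

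**The concern.** A coordinator working from item a.6 reviews AEs when the kit is handed over. A coordinator working from the Appendix D grid does so at a follow-up visit that, under section 6.3, non-local patients do not have. At the visit they do attend, the next of Visits 2 to 5, the grid prompts no AE question.

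The protocol uses this information. Under section 6.10, a patient with a rash or significant AE due to study medication is not randomized again if later found positive. Non-local patients become candidates for re-randomization from their Visit 2, 3 and 4 swabs, so the rule needs an answer that the schedule does not ask for. The cumulative safety review described with serious-event reporting in section 6.9.2 and the roughly yearly safety assessment in section VII draw on the same data. The reactions expected in section 18.C.6 are mainly local irritation and dermatitis, which a patient may not mention unprompted months later.

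**Working it through.** The protocol gives no figure of its own to reproduce here. The check has two parts: what each place assigns to a treated non-local patient, and how long after the recording window that patient is next seen.

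**What each place assigns**

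| Contact | Item a.6 (section 6.3) | Appendix D grid | Non-local patient attends? |
|---|---|---|---|
| Dispensing visit | AE review | blank | yes, but before exposure for a first course |
| Monthly colonization follow-up | none | AE review | no under section 6.3; yes under the Appendix D footnote |
| Visits 2 to 5 | none | blank | yes |
| Infection visit | only if drug is received there | blank | only if an infection occurs |
| Additional/unscheduled visit | only if drug is received there | AE review | not guaranteed |

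Reading item a.6 as the dispensing visit is supported by item a.5 of the same list, which treats dispensing for a positive colonization result as an unscheduled visit. For a repeat course, a review at dispensing could look back at the earlier course, but only in patients who test positive again. Someone dosed after Visit 4 leaves the study at Visit 5 with no AE review marked.

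The AE row in Appendix D carries three asterisks while the AE text stands under two. I matched them by content and place no weight on this.

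**When the window closes**

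Inputs: culture result 3 to 4 days after the swab and randomization 0 to 7 days after the result (section 6.3); 7-day course and 10-day window (section 6.9). Dispensing on the day of randomization is my assumption.

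Days from swab to close = culture + randomization + course + window.

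- Earliest: 3 + 0 + 7 + 10 = day 20.
- Latest: 4 + 7 + 7 + 10 = day 28.

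**When a non-local patient is next seen**

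Scheduled visits are 6 months apart, each with a window of 2 months either way. The 28-day month is defined for the monthly swabs and it is unclear whether it extends to these visits, so I use 28 and 30.44 days.

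- Swab at Visit 1, next visit at month 4 to 8:
  - 28-day months: 112 − 28 = 84 to 224 − 20 = 204 days after the window closes.
  - 30.44-day months: 121.76 − 28 = 94 to 243.52 − 20 = 224 days.
- Later visit pairs, both windows at their extremes (2 to 10 months apart):
  - 28-day months: 56 − 28 = 28 to 280 − 20 = 260 days.
  - 30.44-day months: 60.88 − 28 = 33 to 304.4 − 20 = 284 days.

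That is about 3 to 7 months after Visit 1 and about 1 to 9 months for later pairs.

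**Local patients, for comparison**

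The first follow-up falls at day 21 to 35 (28 ± 7). Counted from the swab, this is from 7 days before the window closes (21 − 28) to 15 days after (35 − 20). Counted from dispensing, where the window closes at 7 + 10 = day 17, it is 4 to 18 days after. Appendix D marks AE review at this visit.

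**The case against.** The strongest reply is that the protocol does provide for these patients. The interview sentence in section 6.9 can be read to cover the next 6-month visit. The Appendix D footnote calls for AE review in everyone given active or placebo, without regard to residence. If Appendix D governs in full, its footnote also brings non-local patients back for monthly visits, where the review is marked. The 10-day limit can define which events count rather than when to ask, so a later interview could still record a qualifying event. Serious events have their own immediate reporting route, and the chart review at each 6-month visit covers medical conditions and hospitalizations.

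Much of this stands. A reader might infer that treated non-local patients have no AE review at all after exposure. The documents do not support that: they conflict, and an unscheduled visit could also supply a review. But each rescue requires choosing one text over another or giving an undefined term a particular meaning, and none puts an AE prompt at Visits 2 to 5. Chart review and serious-event reporting are unlikely to find a mild rash that nobody asked about.

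Two other inferences should be set aside:

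- **That local patients are missed as well.** They have a marked review close to the end of the window, and asking then about a 7-day topical course is ordinary recall.
- **That adherence timing is contradictory, so a null efficacy result could not be interpreted.** Section 5.1 places the questionnaire after the course, item a.7 at the visit following therapy, and section 6.3 says "Adherence to the study medications will be assessed at the next scheduled study visit by a patient questionnaire". These are compatible. Every treated patient is asked, although non-local patients are asked late.

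**Conclusion.** The inconsistency is real and should be corrected. Item a.6, section 6.9 and Appendix D give different answers on when AE review takes place, and the local-only rule in section 6.3 conflicts with the Appendix D footnote. As a result, no scheduled visit after exposure is assured to include an AE review for treated non-local patients. They are next seen about 3 to 7 months after the window closes (84 to 224 days) when treated after Visit 1, and about 1 to 9 months after (28 to 284 days) for later visit pairs.

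These intervals assume dispensing on the day of randomization and visits within their stated windows. The number of patients affected cannot be computed: the non-local share is not given, and section 5.2 says that San Antonio Military Medical Center enrols local patients only. Section VII specifies no between-arm AE test, so what is at stake is the completeness of the safety data and the working of the section 6.10 restriction, not a planned comparison.

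**What to change.** Reconcile the three places so that they give one answer:

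1. In Appendix D, mark AE review at Visits 2 to 5 for any patient dosed since the previous visit, to be completed before any re-randomization that follows from that visit.
2. Change item a.6 in section 6.3 from the dispensing visit to the first contact after the course.
3. In section 6.9, name the visits meant by medical follow-up, and state that the 10-day limit refers to when the event occurred, not when the patient is asked.
4. Make the Appendix D footnote on monthly swabs and the local-only rule in sections 5.1 and 6.3 agree.

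The cost is text and form edits and a few extra questions at existing visits; no visit or test is added. The limitation is that events in non-local patients will still be reported by recall, often months later. A take-home form covering the course and the following 10 days could reduce that. It is optional, would need reminders when not returned, and should supplement the investigator interview, since section 6.9 specifies an interview and section 6.9.2 requires a graded judgement of relatedness.

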6.9.1 Grading Adverse Events for Severity

All AEs will be graded for severity. Selected AEs will be graded in severity as defined in **Attachment A**. Adverse events will be graded as mild, moderate, severe, life-threatening, or fatal. Mild adverse events (grade 1) are often transient, do not interfere with subject's usual function and no intervention may be required. Moderate adverse events (grade 2) interfere to some extent with usual function; there may be some impairment of functioning without resulting in loss of work or cancellation of social activities. Grade 2 adverse events are uncomfortable or an embarrassment. Severe adverse events (grade 3) significantly interfere with usual function, may require bed rest and/or result in loss of work or cancellation of social activities. Grade 3 adverse events produce significant impairment of functioning or incapacitation, and medical intervention is often required. Life-threatening (grade 4): adverse events result in extreme limitation in activity, significant assistance is required and immediate medical intervention or therapy is required to prevent death.

6.9.2 Relatedness of Adverse Events to the Study Drugs

Any AE that occurs in a patient/study subject receiving study medications will be assessed for relationship to the drug/investigational product. A causal relationship means that the drug/ investigational product caused or is reasonably likely to have caused the AE. This usually implies a relationship in time between the drug/ investigational product and the AE—for example, the AE occurred shortly after the patient/study subject received the drug/investigational product.

The best estimate at the time of reporting of the causal relationship between the experimental intervention and an adverse event and the degree of certainty about causality will be graded as follows:

Definitely Related: The adverse event and administration of study agent are related in time, and a direct association can be demonstrated (e.g., disappears or decreases with reduction in dose or cessation of drug/investigational product and recurs with re-exposure).

Probably Related: The adverse event and administration of study agent are reasonably related in time and/or follows a known pattern of response, and the adverse event is more likely explained by study agent than other causes.

Possibly Related: The adverse event and administration of study agent are reasonably related in time and/or follows a known pattern of response, and the adverse event can be explained equally well by causes other than study agent (e.g., could readily have been produced by the subject's clinical state or could have been due to environmental or other interventions).

Unlikely Related: A potential relationship between study agent and the adverse event could exist (i.e., the possibility cannot be excluded), but the adverse event is most likely

explained by causes other than the study agent (e.g., could readily have been produced by the subject's clinical state or could have been due to environmental or other interventions)

Not Related: The adverse event is clearly due to extraneous causes (e.g., underlying disease, environment) or exposure to the investigational product has not occurred. Such events MUST have an alternative, definitive etiology documented in the patient's medical record.

Serious adverse events (SAEs) are adverse events, whether related to the study agent or not, that result in: 1) death, 2) threat to life, 3) inpatient hospitalization or prolongation of existing hospitalization, 4) persistent or significant disability or incapacity, 5) congenital anomaly or birth defect, 6) overdose, or 7) any medical event which requires treatment to prevent one of the medical outcomes previously listed.

SAEs and subject discontinuations will be reported to the Medical Monitor. Each subject will be carefully observed for signs of intolerance or toxicity. If any adverse reaction is noted, the subject will be treated as medically indicated. The subject may be withdrawn from the study if it is felt by the clinical investigators that the subject is at an undue risk from further participation.

The Site Principal Investigator will report any serious or unexpected adverse reactions immediately to the Medical Monitor. Within 24-48 hours the Site Principal Investigator will also use telephone or fax transmission to notify the IRB at their site (timeframe depends on local IRB requirements) and Lead Principal Investigators at which time the Lead Principal Investigator and the site Medical Monitor will determine if the study should continue. The Medical Monitors and the Principal Investigator (PI) will be responsible for reviewing the cumulative safety data.

Any event, whether expected or unexpected, that is classified as a SAE which is fatal or non-fatal will be reported within 48 hours to the USU IRB once the PI is made aware of the event. Non-serious adverse events related to the receipt of the study medication will be reported at time of the continuing review.

Submission of serious and unexpected adverse experiences is the responsibility of the Principal Investigator.

6.10 Termination

A subject's participation will be terminated if one of the following occurs:

- a. Subject voluntarily withdraws
- b. Subject fails to comply with study procedures
- c. Decision in the best interest of the patient
- d. Patient is no longer eligible for care at the military HIV clinics
- e. Patient becomes pregnant or decides to become pregnant during the two-year study period

- f. The patient begins employment as a healthcare worker with direct patient contact

A subject who develops a rash or significant adverse event due to study medication will be discontinued from treatment but will be encouraged to continue to undergo follow up including study visits for completing questionnaires and swabs for MRSA colonization every 6 months (+/- 2 months) until study completion; the patient will not be randomized to one of the treatment arms if he/she is found to be positive again for MRSA colonization. The subject may be withdrawn from the study if it is felt by the clinical investigators that the subject is at an undue risk from further participation.

The subject will require a termination visit if withdrawn from the study. If a subject's participation in this study is terminated, they will be offered medical standard of care and a medical evaluation, to include clinical laboratory studies as needed. The investigator will complete the Completion/Discontinuation CRF.

VII. STATISTICAL ANALYSES

There are four primary questions to be answered to address this study's primary objective. These, and an analysis designed to answer the question, follow.

- (1) What is the hexachlorophene/mupirocin treatment effect to clear MRSA colonization compared to placebo? We will also examine if these decolonization procedures are effective at reducing MRSA infections and skin/soft tissue infections compared to placebo. We propose to pool the data at 6, 12, 18, and 24 months as if they were independent and conduct a chi-square or Fisher's exact test of contingency. These analyses will be conducted for colonization and infection separately. The proposed pooling of this study design assumes that there is no persistent or repeated-treatment effect and that there is no patient-to-patient difference in susceptibility. These effects will be investigated in the following questions.
- (2) Is the treatment effect different for repeat administrations of hexachlorophene/mupirocin? The rate of MRSA positive versus negative for recolonization reoccurrence through the sequence 1 versus 2 versus 3 versus 4 treatments will be assessed by a test of trend.
- (3) Is there a persistent or repeated-treatment effect? The overall rates of MRSA recolonization at 6, 12, 18, and 24 months will be assessed by a test of trend.
- (4) Is there an individual propensity for susceptibility and what are the treatment differences between placebo and hexachlorophene/mupirocin in terms of length of time for being negative for MRSA colonization on repeated testing? A Kaplan-Meier long-rank test will be conducted on three groups: initially negative, initially positive treated with hexachlorophene/mupirocin, and initially positive treated with placebo, where survival is defined as not having acquired MRSA.

For the secondary objectives, part (a) will be assessments of the rates in which prevalence is defined as the number of patients colonized with MRSA at the beginning of

the study divided by the total population studied, and the incidence as the number of new infections per calendar time divided by the total population studied. For objective (b) examining for predictors of MRSA, we will create a multivariate logistic regression model and use a backward stepwise approach. For part (c), to evaluate if there is a significant change in the CD4 count and/or viral load pre- versus during a MRSA infection we will utilize a 1-way ANOVA. We will also compare pre-MRSA infection with after MRSA resolution as well as the counts during the infection with those after resolution. Finally, objective (d) will be a descriptive analysis of the molecular and microbiologic characteristics of the isolates. The main statistical data from the retrospective chart review study of HIV patients at NMCSD will be presented by descriptive analyses. We will compare demographics and HIV clinical data between those with and without MRSA using rank sum tests and Fisher's exact tests depending on the variable characteristics (categorical or continuous). A multivariate logistic regression model for predictors of MRSA will then be developed using a backward stepwise approach using Stata software.

The sample size calculation for this study is based on the primary objective of the study which is to evaluate the effectiveness of decolonization procedures with application of nasal mupirocin (Bactroban®) and hexachlorophene (pHisoHex®) soaps compared to placebos with no antibacterial activity among patients found to be colonized with MRSA in the prevention of future colonization with MRSA. We will also examine the number of infections with MRSA and soft tissue infections as secondary measures of the primary objective.

The rate of MRSA colonization of the nares was 1% in a recent study involving the general US population [41]. Among HIV-infected patients this rate is higher, with one study showing a carriage rate of 27.6% [11]. However, other studies had rates of 3-9% among their HIV-infected patients [26, 27, 42]. The MRSA infection rate among HIV-infected persons is approximately 13 cases/1000 person-years in one study that examined 3,455 patients over three years with 94 MRSA infections [7]; our rate at NMCSD appears higher with 40 cases/1000 persons in the year 2005 [12].

In a study examining both MSSA and MRSA colonization rates, after treatment with mupirocin (Bactroban®), colonization was eradicated in 93%, whereas 85% who received placebo remained colonized ($P < .001$). At day 90 after study entry, 61% of the residents in the mupirocin group remained decolonized [36]. In a study by Ellis et al involving 812 soldiers over a 8-10 week period of training, of those with MRSA colonization without treatment for decolonization, 38% developed a soft tissue infection [43].

Using these data, assuming 10% of the HIV patients would be colonized, that half would be randomized to each treatment group, and that 85% in the non-treatment arm would remain colonized versus 7-39% (mean 23%) of the treated would remain colonized, we calculated the following sample sizes:

Colonization rate of the	Power	Alpha level	Sample size per group	Total sample size
--------------------------	-------	-------------	-----------------------	-------------------

Treated Group				
0.07	.80	.05	80	160
0.23	.80	.05	120	240
0.39	.80	.05	210	420

Hence to show a statistically significant decline in colonization rates using mupirocin (Bactroban®) and hexachlorophene (pHisoHex®), up to 420 patients would be required. Given potential lost to follow-up events and that the colonization rate or clearance rates may vary, we propose to enroll 550 participants, such that 500 participants are followed throughout the study period. Given this sample size and the estimate of a 10% colonization rate over the study period, we would estimate that 50-55 participants will be randomized. Since participants with repeat colonization events may differ from those with first time MRSA colonization and may differ in response to decolonization medications, we will also examine as a secondary analysis of the primary endpoint only those with unique randomizations.

For showing a significant difference in the number of infections between the two treatment groups, assuming 38% of the no specific treatment group and 10% of the treatment group will develop infection, a sample size of 860 would be needed; of note, this is a secondary objective and not the primary basis of the sample size calculation for this study. For smaller changes in the difference in the rates between groups, larger sample size would be needed. Of note, the first rates (38% vs. 10%) were determined during an 8-10 week period and our study involves 6-month periods over a total two year period; on the other hand, this military training population studied for these estimates may have a higher rate than our HIV patients.

Infection Rate in Treated Group	Infection Rate in Placebo Group	Difference in Infection Rate Between Groups	Power	Alpha level	Total sample size for one time period	Total sample size for every 6 month evaluations
10%	38%	28%	.80	.05	860	277
10%	30%	20%	.80	.05	1440	464
10%	25%	15%	.80	.05	2260	729
5%	15%	10%	.80	.05	3200	1032

To account for the study design of patients being re-examined every 6 months over a two-year period (a total of five visits) and re-randomized at each of these intervals with new infections being counted as separate events, the sample size required was notably smaller (last column in table). The calculations accounted for a progressive decrease in colonization and infection rates over the course of the study since patients would be given decolonization medications depending on their randomization assignment.

Using these data, we proposed a sample size of 500 participants to find statistically significant results; given the long duration of follow-up and the possibility for attrition, we will enroll 550 participants accounting for 50 drop-outs.

Overall, we plan to enroll 550 participants into the study with the goal of a minimum of 50 randomizations for scientific significance. In addition, we will also examine unique randomizations, defined as a subject's initial randomization (not counting re-randomizations), as a sub-analysis of the primary endpoint. Of note since the primary endpoint includes completion of the 6 month follow-up visit after initial randomization, at least 50 subjects with these data are needed.

We plan to conduct an interim examination yearly (after at least one-half of subjects are enrolled) to determine the adequacy of the design assumptions and sample size, given that there is little literature regarding the expected colonization and infection rate in this specific (HIV) population. Also, approximately every year we will conduct an examination of the epidemiologic data regarding the prevalence and incidence of MRSA in this cohort, as well as a safety assessment.

We also calculated a sample size for the secondary objective which was to determine the predictors of MRSA colonization and infection among HIV-infected persons including examination of demographics, sexual activity, hygienic procedures, drug use, antibiotic and HAART medications, sexually transmitted diseases and HIV control. Of note, the other secondary objectives do not lend themselves to sample size calculation due to the paucity of baseline data in the literature. Predictors for MRSA were examined in three studies including Mathews et al, Lee et al, and our retrospective work [7, 12, 13]. For a power at 80%, alpha of 0.05, and examining 20 potential predictors with an R^2 of 0.10, we would need to enroll 205 patients in the study (sample power analysis, SPSS). As we examined more predictors, a larger sample size (500 to 550) is preferred.

VIII. DATA ENTRY AND ANALYSES

The IDCRP Data Coordination Center (DCC) will enter completed CRF data and manage all study data. In order to comply with requirements of maintaining subject confidentiality, only the subject's participant identification number (PIN) will be used to identify the research information (as detailed below in section IX). A computer program generates the PIN number randomly. The DCC Data Management Specialist will be the only one authorized to have access to view full identifying information within the database. The individuals with access to the data will be study coordinators designated by the PI of the project and the site PI according to the agreed upon data management plan. Regulatory staff from the Regulatory Compliance and Human Subjects Protection Branch (RCHSPB)/SAIC-Frederick, Inc. will also have access to view full identifying information during monitoring visits and auditing. After data entry, data will be analyzed using SPSS 13.0 and SAS 8.0 for the purpose of publication of significant study findings; these publications will not disclose personal information such as patient names. The data and CRFs will be maintained as per local IRB requirements.

IX. STORING AND DISSEMINATION OF DATA

Upon enrollment, each subject will be assigned a unique participant identification number (PIN), which will include no patient identifiers. A patient will be assigned a PIN centrally once the patient agrees to participate in a IDCSP study. If a patient agrees to participate in other IDCSP studies, this same PIN will be used to link that patient to these other studies. For instance, if a patient is already enrolled into the Natural History Study, the same PIN will be used for all future IDCSP studies. This PIN and the data collected will be maintained in a secure password protected database at DCC. The master link between the new PIN for this study and the patient's identifying information will be kept by the Study Coordinators at each site in a locked, secure location. The master link will be maintained at DCC after the study's conclusion. In addition, each participant will be assigned a unique study identification number designating the clinical site of enrollment and a number assigned to that specific individual.

During the study, CRFs from each patient will be stored in a locked file cabinet in the office at each clinical site. In order to comply with requirements of maintaining subject confidentiality, only the subject's study number will be used to identify the research information.

It is expected that these data will be reported in both scientific journals and scientific meetings. Confidentiality of subjects will be maintained in all forms of reporting. Volunteers will be informed in general terms of the results as soon as practical.

The trial will be conducted in compliance with this protocol, International Conference on Harmonization (ICH) Guideline for Good Clinical Practices (GCP) and any applicable regulatory requirement(s). Monitors under contract to the NIAID will visit the clinical research site to monitor all aspects of the study in accordance with the appropriate regulations.

The objectives of a monitoring visit are as follows:

- To verify the prompt reporting of all data points, including reporting SAEs, checking availability of signed informed consent;
- To compare individual subjects records, Case Report Forms (CRFs) and the source documents (supporting data, laboratory specimen records and medical records to include physician progress notes, nurse' notes, subjects' hospital charts); and
- To ensure protection of study subjects, compliance with the protocol, and accuracy and completeness of records.

The monitors will also inspect the clinical site regulatory files to ensure that regulatory requirements (OHRP/ICH-GCP) are being followed. During the monitoring visits, the investigator (and/or designee) and other study personnel will be available to discuss the study progress and monitoring visit.

The investigator (and/or designee) will make study documents (e.g., consent forms, CRFs) and pertinent hospital or clinical records readily available for inspection by the local IRB,

the site monitors, and the NIAID staff for confirmation of the study data.

X. FACILITIES TO BE USED

